To accomplish these goals, our outpatient clinic is open Monday thru Friday offering 4 different appointment times. All patients that are referred to our clinic for TAP, first receive a vein evaluation to see if the patient is a candidate for peripheral IV therapy. At our clinic, approximately 68% of our TAP's are performed peripherally. This eliminates the risk of a central line infection and any alteration in activities of daily living, such as bathing(Kramer, 2016), (Shang, Ma, Poghosyan, Dowding, & Stone, 2014),(Keller et al., 2018; McDiarmid, 2015).

Our hypothesis, is that the 20-gauge BD Nexiva Diffusics catheter provides the same efficacy as current practice with no increase in adverse events for patients undergoing therapeutic apheresis. The results from our study will be significant because if the 20 guage needle is equally effective for TAP, it can increase the number of patients that would be candidates for peripheral therapy. Therefore, decreasing the need for central venous access, which place the patient at an increased risk of infection. Our study is a comparison of 2 types of infusion catheters. The standard of care is an 18-gauge autogard catheter (control group) which will be compared to the 20-gauge BD Nexiva Diffusics (intervention).

- P patients who require therapeutic apheresis procedures (TAP)
- I use of 20G BD diffusics catheter during apheresis
- C use of 18 G standard of care IV catheter during apheresis
- O no difference in efficacy and no increase in safety events

Concise Summary of Project

This is a randomized pilot study of TAP using the current standard of care catheter (SOC) vs the BD Nexiva Diffusics Catheter. It is a single blinded, randomized study. Data will be used to refine and power a full randomized control trial. For this study, a sample of 33 encounters in each group (total of 66 encounters). Our specific aim is to test the hypothesis that the 20-gauge BD Nexiva Diffusics Catheter provides the same efficacy and lower pain level with no increase in adverse events for patients undergoing apheresis treatments.

Randomization Procedure

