After an eligible participant is consented to the study the patient will be randomized without replacement to the use of one of the two catheters. Using a random number generator, numbers between (1-66) were randomly divided into two groups: SOC Control group and BD Intervention group (Figure 1). A study identification number (SID) key will be saved on a UTSW approved secure device and only the research coordinator will have access to the SID key showing which SID coordinates with each group. This will ensure that unblinding can occur is necessary and there is a backup to randomization.

The research coordinator will have 66 randomized envelops without replacement. Half of the envelops will be assigned to 18G catheter SOC (control) and the other half be assigned to

20G BD Nexiva Diffusics catheter (intervention). The PI will be blinded, therefore the PI will pick an envelope when patients are consented and ready for treatment. Participants will be randomized after they have consented to the study. Participants' will then be randomized to one of the two groups again at each encounter (i.e., SOC visit). Inside the envelope it will tell the investigator if the patient is in the control or intervention group of the study.

To promote a more representative sample, each patient may participate a maximum of 10 times.

Study procedure:

[figure not shown]
Each enrolled patient will participate in the study will be randomized at each encounter. During each encounter the following information will be captured:

- 1. CBC
- 2. Patient discomfort

level with placement of catheter

- 3. Inlet rate
- 4. Return line pressures
- 5. Procedures alarms
- 6. Procedure total time
- 7. Post procedure sample

Treating nurse (RN) will start the TAPs procedure with one of the 2 catheters. During the intervention period, the RN will be at bedside during as it is SOC in the Apheresis unit however for the purpose of this study the RN will have the study data collection form (DCF, Appendix1). The RN will complete the pre-assessment including a pain assessment to establish pain level prior to procedure that is currently documented in the electronic medical record. The patient will be asked to self-report the pain level after the return line has been started on the visual analog scale (VAS) Scale from 0mm to 100mm "0 being the lowest/ no pain, 100mm being the highest

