level of pain". The VAS scale will be used for both the SOC and intervention group to compare the pain level when starting the return line. The RN will collect a CBC before the start of the procedure which will be used in the programing of the TAP procedure. The RN will start recording the "inlet rate, return line pressures, and alarms" every 15 minutes until the procedure is completed.

Before patient disconnects, and after the completion of procedure sing the same therapeutic apheresis procedure access site, a blood sample will be drawn by the RN 2 lavender top tubes (4ml) for plasma hemoglobin test. The plasma hemoglobin test will be sent to the UTSW lab for analysis of hemoloysis and results will be sent back directly to the PI. Blood sample results will be collected by the PI or the study team in an excel spreadsheet (CRF) that will be saved on a secure drive on the UTSW campus.

Hemolysis is defined as the destruction of red blood cells which leads to the release of hemoglobin from the red blood cells into the blood plasma. Each patient will be tested for hemolysis by running plasma hemoglobin test after the procedure has finished. This will be collected in a two lavender tops (4ml) The cost for this test is covered by sponsor and because the patient has an indwelling access to venous blood there will no charge for drawing the sample.. There is no clinical suspicion that the use of the 20-gauge BD Nexiva Diffusics Catheter will increase this risk. Hemolysis will be scored dichotomously as present or absent for each encounter.

Pain is defined as any increase discomfort experienced by the patient associated with the apheresis procedure. The current standard of care is to ask the patient "are you having pain" and then ask them to rate the pain from 0 to 10. For this study, one additional question will be asked after the patient's vein has been accessed (IV catheter in place). The patient will self-report their pain using a 100 mm VAS scale. "*The VAS has been used by healthcare providers to measure the characteristics of disease severity in each patient individually*"(Klimek et al., 2017) Currently, all peripheral apheresis patients have some pain/discomfort while having a treatment, however; it is usually tolerated with minimal complaints.

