For this study, patients will be recruited from the Apheresis Unit at UT Southwestern University Hospital and Clinics by a member of the research team. A member of the research team will screen the electronic medical record to determine a patient's eligibility. If a patient appears eligible for the study a member of the research team will discuss eligibility criteria with a member of the clinical team (nurse manger, nurse, physician, resident, fellow, social worker). The researcher will communicate with the clinical team to ensure eligibility: adult (≥18 years old), speaks and reads English, admitted to the Apheresis Unit at UT Southwestern University Hospital and Clinics at the time of consent. All patients in this study will be able to provide selfconsent (read and speak English).

When a patient is deemed eligible, a member of the research team will discuss consent and study procedures with that patient, in a place that is comfortable for the patient. After being approached by a member of the research team, patients will have up to next visit to consider participation in the study. The study team expects recruitment of 30 participants to last approximately 8 months. (Table 1)

Potential Benefits

There may or may not be a direct benefit to the participants in this study. Any additional blood test result that seems out of the norm will be shared with the nurse on duty or treating physician. We would also hope to share this with the greater research and clinical community in hopes of finding an alternative way for apheresis patients to have therapeutic apheresis procedures with less pain and no increase in adverse events.

Potential Risks

Risks associated with BD Cather:

Longer procedure time might occur if the inlet rate of the treatment is slower. The patient will be informed of this during the ICF process. With smaller catheters there's a risk of not obtaining the appropriate return rate for the patient. When the return rate is out of the SOC parameters the SOC apheresis equipment (Optia or Cellex) will alarm. If the alarm sounds 3 times the RN will decrease inlet rate by 5 ml/sec until the minimum threshold is reached (if needed), which is 50 ml/sec for plasma exchange and 35 ml/sec for RBC exchange and 20 ml/sec for photopheresis. If the alarm continues to when the minimum threshold is reached the catheter will

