be replaced with the SOC 18-gauge catheter. Obtaining blood samples may cause some discomfort, feeling lightheaded, fainting, bruising, clotting, and bleeding from the site of the needle stick and, in rare cases, infection. The risks are mitigated by drawing blood from a line that has already been established as part of SOC.

There is a low risk of breach in confidentiality. Subjects will be assigned individual study identification (SID) numbers and no personal identifiers will be included in the final summary.

Patients who are randomized to the 20-guage needle group and who fail the intervention will be given the 18-guage standard of care needle. At the patient's next visit, the patient will once again be randomized. If the patient is randomized into the 20-guage needle arm and fails the intervention a second time, the patient will be removed from the study.

Procedures to Maintain Confidentiality

Study participants will be given a study identification (SID) number. Only the approved study personnel and the principal investigator have access to the database linking the SID to the patient name. This database is kept on a protected drive on a password protected computer. Paper or hard copy participant records will be kept in a locked file cabinet in a locked office. If any identifying information is transmitted, it will be done so via secure e-mail and/or dedicated fax machines.

Statistical Analysis Plan

All data will be first collected on the DCF (Appendix I) and then entered into an electronic spreadsheet (e.g., MS Excel) which will be converted to SAS v 9.4 for analysis. All statistical analyses will be performed at UTSW in a location with secure data encryption capability. Initially, the data will be summarized first using standard measures of central tendency (mean, median, standard deviation, and interquartile range) for each variable. These will be examined to support the assumption of being approximately normally distributed. Baseline characteristics will be summarized using appropriate parametric and non-parametric measures.

The primary hypothesis is that the 20-gauge BD Nexiva Diffusics catheter provides the same efficacy of current practice with no increase in adverse events for patients undergoing therapeutic apheresis. This will be examined in 2 steps. First, ANOVA will be used to explore

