efficacy wherein efficacy is represented by 1) the plasma hemoglobin value, and 2) the amount of time (minutes) required to complete a TAP. Hence models will be constructed to compare the mean plasma hemoglobin values by group, and to compare the mean number of minutes to complete TAP by group. Second, ANOVA will be used to compare the mean number of adverse events subjects experience in each group (intervention vs control).

Finally, a planned secondary analysis is to examine if the percent of lumen occupied by the return catheter is associated with return pressures. The suggested standard is that a catheter occupies < 45% of the inner-lumen diameter (measured with ultrasound). Return pressures >400 mm Hg are considered problematic. Chi-square analysis will be used to explore the odds of experiencing a return pressure > 400 mm Hg when the return catheter occupies <45% of the inner-lumen diameter.

Item	Month 1-2	Month 3-6	Month 4-8	Month 9-11	Month 12-18
IRB approval	Х				
Consent/	Х	X			
Enrollment					
Randomization	Х	X	Х	Х	
Data collection	Х	Х	Х	Х	
Manuscript				Х	X
prep					
Study closeout					X

Project Timeline

Enrollment of first patient (month 1), enrollment of the last patient (month 12), completion of data analysis (month 14), and manuscript submission (month 18). The apheresis team see approximatley 3000 TAP treaments each year. Of these, approximately 1500 encounters will meet the primary inclusion criteria. We anticipate that it will take less than 1-year to complete the study.

Future directions

The intention of this pilot study is to test the 20-gauge BD Nexiva Diffusics Catheter performance and efficacy. The findings from this study will be used to provide additional preliminary data to BD to support a National Institutes of Health or Agency for Healthcare Research and Quality (AHRQ) application (pending 2017 AHRQ funding announcements). Stakeholder feedback will be provided through an optional de-identified report to all patients and families.

Presentation of data

It is anticipated that the results from this study will be presented to American Society for Apheresis at their annual convention. The results will also be summarized in a manuscript and submitted for peer-review publication to Journal of Clinical Apheresis.

Appendix 1

Patient Sticker

A Randomized Trial Examining Plasma Exchange using the BD Catheter In an Outpatient Apheresis Unit The "REPLACE" study

Date SID Procedure Type						

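### The only planned test of 'no increase in adverse events' is ANOVA on mean counts, which breaks down if events are rare and cannot show absence of an increase

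*Combined protocol and SAP*

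**What the plan says.** The Statistical Analysis Plan gives the primary hypothesis an efficacy part and a safety part, and adds: "This will be examined in 2 steps". The first step applies ANOVA to plasma hemoglobin and procedure time. The second is the safety step: "Second, ANOVA will be used to compare the mean number of adverse events subjects experience in each group (intervention vs control". The outcome summary in Background and Significance sets the aim as "no difference in efficacy and no increase in safety events".

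On size, the Concise Summary of Project states: "For this study, a sample of 33 encounters in each group (total of 66 encounters". The Randomization Procedure splits the envelopes equally, randomizes again at each encounter, and adds that "each patient may participate a maximum of 10 times". The recruitment section expects 30 participants.

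The documents give no adverse event rate, alpha, non-inferiority margin, confidence interval, exact or count method, or rule for the case of no events. The SAP does plan descriptive summaries of every variable and a look at whether they are roughly normal, but names no alternative analysis if they are not.

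**The concern.** Adverse event counts over 33 encounters per arm may be mostly zeros. A normal-theory F test estimates its error variance from those same counts. If every count is zero there is no variance to estimate. If only a handful are non-zero, the test statistic can take only a few values and the nominal 5% level need not hold.

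The direction of the hypothesis is a second problem. The plan wants to conclude that the 20-gauge catheter brings no increase in events, but an ANOVA p-value above 0.05 shows only that a difference was not detected. With no margin and no interval, the result cannot say how large an increase remains compatible with the data. The pilot is meant to inform the design of a full trial, so an event rate with its uncertainty would be more useful than a p-value.

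**Working it through.** **Inputs from the documents:** 33 encounters per arm, 66 in total, equal allocation. **Assumptions, because the documents are silent:** two-sided alpha 0.05; event rate 0.01 to 0.20 per encounter; the encounter as unit. The plan states no figure for this test, so there is nothing to reproduce.

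**1. No events.** Between- and within-arm sums of squares are both 0, so F = 0/0. With Poisson counts, P(no event) = exp(−66 × rate): exp(−0.66) = 52%, exp(−1.32) = 27%, exp(−1.98) = 14%, exp(−3.3) = 3.7%, exp(−6.6) = 0.1% at rates 0.01, 0.02, 0.03, 0.05 and 0.10.

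**2. A few encounters with one event each, all in one arm (0 v k).** Between-arm sum of squares = k²/66; within-arm = k − k²/33, on 64 df. Hence F = 64 × (k²/66) / (k − k²/33) = 32k/(33 − k). The 5% critical value of F(1, 64) is 3.99. The two-sided Fisher p-value is 2 × C(33,k)/C(66,k).

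| k | F | ANOVA p | Fisher p |
|---|---|---|---|
| 3 | 96/30 = 3.20 | 0.078 | 0.238 |
| 4 | 128/29 = 4.41 | 0.040 | 0.114 |
| 5 | 160/28 = 5.71 | 0.020 | 0.053 |
| 6 | 192/27 = 7.11 | 0.010 | 0.024 |

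**3. Type I error given the total number of single-event encounters.** Under no catheter effect, every split of the affected encounters follows the hypergeometric distribution. With 1 to 3, no split reaches F = 3.99, so the error is 0%. With 4, only 0 v 4 and 4 v 0 reject: 2 × 40,920/720,720 = 11.4%. With 5 it is 5.3% and with 6 it is 2.4%. With 7, the split 1 v 6 also rejects (p=0.046) and the error rises to 10.5%.

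**4. Type I error averaged over totals** (0/1 events, exact enumeration):

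| Rate per encounter | 0.01 | 0.02 | 0.03 | 0.05 | 0.10 | 0.20 |
|---|---|---|---|---|---|---|
| ANOVA | 0.05% | 0.4% | 1.2% | 3.3% | 5.6% | 5.2% |

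Simulated Poisson counts (60,000 trials per rate) give 0.06% to 3.0% at rates up to 0.05, and 4.7% to 5.3% from 0.10 to 1.0.

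**5. What a non-significant result would mean.** In the same kind of simulation, ANOVA detects a doubled Poisson rate with power 5% from a control rate of 0.03, 10% from 0.05, 18% from 0.10 and 31% from 0.20. A true doubling would usually be missed.

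**6. What an interval says with no events.** For 0 of 33, the exact two-sided 95% upper limit is 1 − 0.025^(1/33) = 10.6%.

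**The case against.** The best defence is that the harm is conditional and modest. Averaged over event totals, ANOVA does not reject too often at low rates, and from about 0.10 events per encounter its error is close to 5%. Fisher's test is itself very conservative (by the same enumeration, 1.2% at a rate of 0.10 and 2.4% at 0.20), so part of the gap between the p-values reflects that. The study is a pilot with no stated decision rule, and zero events would still appear in the descriptive summaries. All of this stands, and it limits the point to the case of rare events and to what a difference test can show. It does not supply a fallback, and the plan still presents this ANOVA as its test of half the primary hypothesis.

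Four stronger readings are tempting and are not supported:

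- **That events are known to be rare.** A reader might infer this from "There is no clinical suspicion that the use of the 20-gauge BD Nexiva Diffusics Catheter will increase this risk". That sentence concerns hemolysis alone, and a change in its risk; it gives no absolute rate for any event.
- **That ANOVA disregards how many events an encounter has.** The count is the outcome. Five events against none give p=0.020 as five singles, 0.091 as 2+2+1, 0.164 as 3+2 and 0.321 in one encounter. Only when a single encounter carries all the events does the number cancel (F = 1, p=0.321).
- **That the test fails whether the unit is the patient or the encounter.** The SAP sentence speaks of subjects, but every calculation here is per encounter, so nothing is shown for patients.
- **That repeat patients inflate the error.** With catheters re-randomized at each encounter, simulations with 7, 10 or 30 patients at rates 0.1 and 0.2 gave 3.4% to 4.6%.

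**Conclusion.** The point holds conditionally. If adverse events occur at about 0.05 per encounter or less, the planned test has a 3.7% (at 0.05) to 52% (at 0.01) chance of being incomputable, is conservative on average (size 0.05% to 3.3%), and has an error rate between 0% and 11.4% depending on how many single-event encounters occur. From about 0.10 per encounter its average calibration is acceptable. Which case applies cannot be told from the documents, which neither define an adverse event nor give a rate; if machine alarms counted, events might not be sparse, but nothing says that they do.

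The second limb does not depend on the rate: without a margin or an interval, a non-significant ANOVA cannot support a claim of no increase. The figures assume independent encounters except in the simulations with repeat patients. The change should be made, since a better analysis is available at almost no cost.

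**What to change.** Replace the ANOVA as the main safety analysis. By assigned catheter, report:

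- total adverse events, beside the number of encounters with at least one event;
- the risk difference for encounters with at least one event, with an exact 95% CI;
- if an arm has no events, the exact upper limit (10.6% for 0 of 33, two-sided 95%).

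State that these intervals treat encounters as independent, and add a sensitivity analysis that allows for repeat encounters by the same patient. With 66 encounters and 30 expected participants, the average is 66/30 = 2.2 encounters each.

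Showing the two counts side by side makes a cluster of events in one encounter visible. A permutation test on total events would not do so: with one affected encounter every re-draw gives the same absolute difference, so p=1. An exact Poisson test is not a safe substitute either. With overdispersed counts (gamma shape 0.3) it rejected a true null 8.1% of the time at 0.2 events per encounter and 18.4% at 0.5, against 4.3% for ANOVA at both.

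The cost is SAP wording and standard SAS procedures. The downside is that exact methods are more conservative, so they are less likely to flag a difference when events are few.

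### The exploratory test of return pressure on lumen occupancy is not split by catheter gauge; a table by gauge is a cheap addition that keeps gauge apart from vein fit

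*Combined protocol and SAP*

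**What the plan says.** The Statistical Analysis Plan describes a planned secondary analysis of whether "the percent of lumen occupied by the return catheter is associated with return pressures". It takes 45% of the inner-lumen diameter, measured by ultrasound, as the suggested occupancy standard and treats return pressures above 400 mm Hg as a problem. The method is one sentence: "Chi-square analysis will be used to explore the odds of experiencing a return pressure > 400 mm Hg when the return catheter occupies" less than 45% of that diameter. The analyses just before it (plasma haemoglobin, procedure time, adverse events) are all stated as comparisons between the randomised groups. This one mentions no group, stratum or adjustment, and no other section supplies one.

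Other sections that bear on the point:

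- Background and Significance hypothesises that the 20G "provides the same efficacy as current practice".
- Potential Risks says smaller catheters carry "a risk of not obtaining the appropriate return rate for the patient". It also provides that, in a setting of persistent alarms, the catheter will "be replaced with the SOC 18-gauge catheter".
- Study procedure has return pressure recorded "every 15 minutes until the procedure is completed".
- Randomization Procedure states that "each patient may participate a maximum of 10 times".
- Appendix 1 records catheter type, three vein-diameter readings, return pressures, alarms and comments.

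**The concern.** Occupancy depends on two things: the size of the catheter and the size of the vein. Randomisation sets the first. In a given vein the 20G falls below 45% more readily than the 18G, so the low-occupancy row of a pooled table will tend to hold more 20G encounters. If the narrower catheter also produces more readings above 400 mm Hg, gauge is a common cause of exposure and outcome. The pooled odds ratio then moves upward for a reason unrelated to vein fit, and meeting the suggested standard looks harmful or less protective than it is.

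The results are meant for a journal and as preliminary data for a grant application (Presentation of data; Future directions). A reader could take the pooled odds ratio as the effect of vein fit for a chosen catheter. The primary comparisons do not depend on this analysis.

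**Working it through.** The documents give no event rate, occupancy share, significance level or power for this analysis, so there is no planned figure to reproduce. The only documented input is 33 encounters per arm, 66 in total (Concise Summary of Project). Everything else below is assumed.

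**Pooled odds ratio when occupancy has no effect within either gauge**

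Let l be the share of encounters below 45% occupancy and p the risk of a reading above 400 mm Hg, each with a subscript for gauge. With equal arms:

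- risk at low occupancy = (l18·p18 + l20·p20) / (l18 + l20)
- risk at high occupancy = ((1−l18)·p18 + (1−l20)·p20) / (2 − l18 − l20)

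For p = 5%/20% and l = 50%/90% (18G/20G throughout):

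- low: (0.5×0.05 + 0.9×0.20)/1.4 = 0.205/1.4 = 14.64%
- high: (0.5×0.05 + 0.1×0.20)/0.6 = 0.045/0.6 = 7.50%
- odds ratio: (0.1464/0.8536)/(0.075/0.925) = 2.12, against a true within-gauge value of 1.00

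The other scenarios use the same formulas. Rejection is for the pooled uncorrected chi-square at 5%, simulated 400,000 times with 33 independent encounters per arm (Monte Carlo standard error at most 0.04 points).

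| p 18G/20G | l 18G/20G | Risk, low vs high occupancy | Pooled OR | Rejection |
|---|---|---|---|---|
| 5%/20% | 50%/90% | 14.64% vs 7.50% | 2.12 | 7.7% |
| 5%/20% | 60%/80% | 13.57% vs 10.00% | 1.41 | 4.4% |
| 5%/20% | 70%/80% | 13.00% vs 11.00% | 1.21 | 3.4% |
| 5%/20% | 70%/70% | equal | 1.00 | not simulated |
| 5%/10% | 50%/90% | 8.21% vs 5.83% | 1.44 | 2.5% |
| 5%/10% | 60%/80% | 7.86% vs 6.67% | 1.19 | 3.0% |
| 5%/5% | any | equal | 1.00 | not simulated |

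These values are not bounds. With higher assumed pressure risks the distortion grows:

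| p 18G/20G | l 18G/20G | Pooled OR | Rejection |
|---|---|---|---|
| 10%/20% | 50%/80% | 1.31 | 5.4% |
| 10%/30% | 50%/80% | 1.54 | 8.6% |
| 10%/30% | 30%/90% | 2.33 | 23% |
| 10%/40% | 30%/90% | 3.02 | about 42% |

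A Cochran-Mantel-Haenszel test stratified by gauge stays below 5% in all nine simulated scenarios. If low occupancy is truly protective (within-gauge odds ratio 0.50), at l = 30%/90% and an 18G risk of 10% at high occupancy, the pooled odds ratio rises from 0.84 to 1.57 as the corresponding 20G risk goes from 20% to 40%. Pooling could therefore hide or reverse the association.

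**Noise and sparse cells**

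At p = 5%/20% the expected events are 33×0.05 = 1.65 in the 18G arm and 33×0.20 = 6.6 in the 20G arm, 8.25 in all. With 0.5 added to each cell, the central 95% of simulated pooled odds ratios runs from about 0.42 to 11.2 (l = 50%/90%) or 0.30 to 8.9 (60%/80%). Sparse-cell results for the split tables:

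| p 18G/20G | l 18G/20G | A zero cell in at least one gauge table | Mantel-Haenszel OR zero, infinite or undefined |
|---|---|---|---|
| 5%/20% | 50%/90% | 86% | 24.6% |
| 5%/20% | 60%/80% | 78% | 13.6% |
| 5%/10% | 50%/90% | 92% | 34% |
| 5%/10% | 60%/80% | 86% | 28% |

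Clustering is not modelled. Recruitment Methods and Consenting Process says "The study team expects recruitment of 30 participants", which gives 66/30 = 2.2 encounters per participant on average, with a maximum of 10.

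**The case against.** The strongest reply is that nothing here is wrong. The plan asks whether occupancy is associated with pressure, calls the test exploratory, and states the 45% standard without reference to gauge. A pooled table answers that question. Within one gauge, occupancy is fixed by vein diameter, so a split table compares wide with narrow veins at a cut that differs between gauges, which is a different question. Both causal links are assumed: the only support in the documents for the second concerns return rate, not pressure above 400 mm Hg, and the stated hypothesis is equal efficacy. The odds ratios depend on the chosen inputs, and the split tables will usually have an empty cell. Nor does splitting by gauge isolate vein fit fully, since procedure types also differ in maximum inlet rate.

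Most of this stands. It makes the point an improvement, not an error, and it is why the pooled table should stay. It does not remove the reason for showing the split. Where both links hold, the pooled odds ratio cannot tell an effect of vein fit from an effect of the catheter under test. Even sparse tables show whether the high-pressure encounters sit in one gauge.

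**Conclusion.** The concern holds as an optional improvement to an exploratory analysis. The plan names no split by gauge, and a pooled odds ratio mixes gauge with vein fit if the 20G both occupies less of the lumen and raises return pressure. With no true effect within a gauge, the pooled odds ratio lies between 1.00 and 2.12 over the lower assumed risks and reaches 3.02 at the highest assumed. It is exactly 1.00 if either link is absent. At the lower risks the pooled test exceeds its nominal 5% in only one of five simulated scenarios and chance dominates; at the higher risks the excess can be large. The documents do not show which case applies. Confidence is medium, because the direction follows from the design but the size rests wholly on assumption.

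**What to change.** Keep the pooled table and add to the Statistical Analysis Plan:

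- The 2x2 table of occupancy below 45% by pressure above 400 mm Hg, shown separately for 18G and 20G, with a gauge-stratified odds ratio (Mantel-Haenszel or exact) where the cells allow. Label it exploratory, and interpret the pooled odds ratio as description only.
- One outcome per encounter: any reading above 400 mm Hg.
- Classification of each encounter by the return catheter first placed, using only readings before any replacement by an 18G.
- Which of the three vein-diameter readings on Appendix 1 defines occupancy. The pooled table needs this too.
- A statement that any interval treats repeat encounters of a patient as independent.

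The core change is one sentence; the definitions add a few lines. No new data are needed: catheter type, vein diameters and pressures are already on Appendix 1, and a replacement can be marked in its Comments column. The costs are sparse cells, so the split tables may serve as description only, and fewer readings from replaced 20G encounters, which have less opportunity to record a high pressure.
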